7.9.4.2. Proportion of Participants with Zero Bleeds

Population	Measurement Period
All participants	≥1 year of follow-up, ≥2 years of follow-up, ≥3 years of follow-up, all available follow-up

For interim and analyses at fixed timepoints, only those with specified amounts of follow-up will be included	
---	--

The proportion of participants who had no bleeding events of each of the following types will be reported and compared between the Roctavian and SoC Cohorts: treated bleeds, major bleeds, life threatening bleeds, and joint bleeds. The approach will be generally consistent with the analysis approach for ABRs (see Section 7.9.3) regarding the adjustment approach (IPTW), analysis of the full follow-up period along with annual increments and start of follow-up period.

The binary outcomes will be analyzed using propensity score IPTW weighted log binomial regression models. The main predictor of interest is the treatment effect (Roctavian vs. SoC), other imbalanced covariates after propensity score adjustment may be included in the model as necessary. The risk ratio (relative risk), corresponding 95% CIs and p-values will be reported.

7.9.4.3. Use of Hemostatic Medications

Population	Measurement Period	Analysis Notes
All participants For interim and analyses at fixed timepoints, only those with specified amounts of follow-up will be included	≥1 year of follow-up, ≥2 years of follow-up, ≥3 years of follow-up, all available follow-up	Participants with no treatment will be included as having a treatment value of 0

Cumulative hemostatic medication use will be compared between the Roctavian and the following SoC sub-Cohorts:

- FVIII treatment use (IU/kilogram [kg])
- Emicizumab treatment use (milligrams [mg]/kg)

The SoC Cohort will be stratified by participants using FVIII treatments and participants using emicizumab. They will separately be compared to the Roctavian Cohort. The amount of total (prophylactic and on-demand) treatments utilized per participant per kg (IU/kg or mg/kg; see Table 4) will be calculated across the follow-up period and calculated between the Roctavian, SoC, FVIII, and emicizumab Cohorts with the same follow-up measurement approach as the primary ABR outcome (see Section 7.9.3). Each participant's average weight over the reporting period will be used when calculating IU/kg. Prophylaxis and on-demand use will be described as available.

The proportion of participants utilizing any hemostatic treatments during follow-up will be described but will not be compared, as 100% of the SoC, FVIII, and emicizumab Cohorts will utilize hemostatic treatments. The use of FVIII for different reasons recorded in the DHR will also be described for each Cohort. For the emicizumab Cohort, the number of injections and regimen utilized (if possible, will be described). The proportion of participants utilizing any hemostatic treatments specifically for bleeds or short-term prophylaxis will be compared regarding the absolute difference in the proportion of participants utilizing a Chi-square test. Similar to the analyses of the proportion of participants with zero bleeding, only those participants with follow-up for the full time over which the proportion is calculated will be included in analyses.

The total annual FVIII per kg during follow-up will be compared between the Cohorts. Total FVIII per kg for any reason will be compared based on the absolute difference in the mean total FVIII per kg between the Roctavian, SoC, FVIII, and emicizumab Cohorts separated by SoC class (PD, SHL, EHL, emicizumab) utilizing a two-sample t-test (two sided). Similar to the analyses of the proportion of participants with zero bleeding, only those participants with follow-up for the full time over which the proportion is calculated will be included in analyses.

Annualized infusion/injection rates (AIRs) will also be compared between the Cohorts. AIRs will be calculated for each participant as the number of infusions or injections divided by the time between the start of follow-up and censoring event for the analysis, annualized to the number of infusions/injections in one year. The mean of the individual participant AIRs for each Cohort will be

calculated and compared. The comparison of AIRs will be based on the absolute difference in the mean AIR between the Cohorts utilizing a two-sample t-test (two sided).

For all the outcomes measuring hemostatic medication use described above, both the unweighted and IPTW weighted analyses will be conducted. SMD will be computed to compare the outcomes between Cohorts. P-values for each corresponding statistical test will also be reported.

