The proportion of participants utilizing any hemostatic treatments during follow-up will be described but will not be compared as 100% of the SoC Cohort will utilize hemostatic treatments. The relative risk of participants utilizing any hemostatic treatments specifically for bleeds or short-term prophylaxis will be compared consistent with the proportion of participants with zero bleeding events. Also consistent with the analysis of the proportion of participants with zero bleeding, only those participants with follow-up for the full time over which the proportion is calculated will be included in analyses.

The total FVIII per kg administered during follow-up will be compared between the cohorts. Total FVIII per kg for any reason will be compared based on the absolute difference in the mean total FVIII per kg between the Roctavian Cohort and SoC Cohort utilizing a two-sample t-test (two-sided). Similar to the analyses of the proportion of participants with zero bleeding, only those participants with follow-up for the full time over which the proportion is calculated will be included in analyses.

Annualized infusion rates (AIRs) will also be compared between the cohorts. AIRs will be calculated for each participant as the number of infusions or injections divided by the time between the start of follow-up and censoring event for the analysis, annualized to the number of infusions/injections in 1 year. The mean of the individual participant AIRs for each cohort will be calculated and compared. The comparison of AIRs will be based on the absolute difference in the mean AIR between the Roctavian Cohort and SoC Cohort utilizing a two-sample t-test (two-sided).

10.3.7.4. Objective: To compare joint health, quality of life, and pain.

Descriptive statistics will be used to summarize the absolute and change from baseline at the time of assessment for the HJHS. A repeated measurement analysis model will be utilized to describe the overall trend in the HJHS over time. The mean change from baseline to final assessment approximately 3 years after index date will be compared between the Roctavian Cohort and SoC Cohort.

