Variable	Captured in DHR	DHR data field name(s)	Operational definition/description
Use of immunosuppression (ever)	Yes	
 Was immunosuppression performed due to the gene therapy If yes: drug type immunosuppression 	
 For participants in Roctavian Cohort, was immunosuppression used (yes/no) Immunosuppressant drugs based on the DHR specified list of immunosuppressant medications
FVIII infusion rate (before index date)	Yes (calculated)	
 Preparation/ medicinal product Frequency Start of reporting period End of reporting period 	
 Number of FVIII infusions during 12-month baseline period Infusion rate will be derived based on the therapy usage and frequency of individual usage periods recorded in the DHR for any reason Data is expected to be able to allow for summaries of AIR To be calculated for FVIII separately (by class) from emicizumab Calculate annualized metric of the number of infusions by dividing the number of infusions by the number of days in the relevant time period, multiplied by 365.25
Prior FVIII utilization (before index date)	Yes (calculated)	
 Occasion Preparation/ medicinal product Consumption/ delivered Weight Start of reporting period End of reporting period 	
 Total IU during the baseline period and annual utilization of FVIII concentrates expressed as IU/kg/year Total IUs received over the 12 months before index date divided by the weight (kg) closest to index date, stratified by occasion of use: bleed (spontaneous hemorrhage), prophylaxis, short-term prophylaxis (intensified on-demand treatment), surgery, ITT, other/unknown Calculate annualized metric of the FVIII usage multiplied by an individualized factor based on amount of prior history (e.g., if 26 weeks of history, multiply by 2), stratified by occasion of use: bleed (spontaneous hemorrhage), prophylaxis, short-term prophylaxis (intensified on-demand treatment), surgery, ITT, other/unknown

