≥2 years follow-up	0	0.0%	0	0.0%	0	0.0%	0	0.0%	0.0000	0.00	0	0.0%	0	0.0%	0	0.0%	0	0.0%	0.0000	0.00
≥3 years follow-up	0	0.0%	0	0.0%	0	0.0%	0	0.0%	0.0000	0.00	0	0.0%	0	0.0%	0	0.0%	0	0.0%	0.0000	0.00
Infusion/ injection rate (number of infusions or injections/year)																				
Mean	0.00		0.00		0.00		0.00		0.0000	0.00	0.00		0.00		0.00		0.00		0.0000	0.00
SD	0.00		0.00		0.00		0.00				0.00		0.00		0.00		0.00			
Median	0		0		0		0		0.0000		0		0		0		0		0.0000	
Q1	0		0		0		0				0		0		0		0			

Measures	Unadjusted							After IPTW												
	Roctavian Cohort		SoC Cohort		FVIII Sub-Cohort		Emicizumab Sub-Cohort		p-value (Roctavian vs. SoC)	Std. Diff. (Roctavian vs. SoC)	Roctavian Cohort		SoC Cohort		FVIII Sub-Cohort		Emicizumab Sub-Cohort		p-value (Roctavian vs. SoC)	Std. Diff. (Roctavian vs. SoC)
	N=		N=		N=		N=				N=		N=		N=					
	N	(%)	N	(%)	N	(%)	N	(%)	N	(%)	N	(%)	N	(%)	N	(%)	N	(%)		
Q3	0		0		0		0				0		0		0		0			
Min	0		0		0		0				0		0		0		0			
Max	0		0		0		0				0		0		0		0			
AIR																				
Mean	0.00		0.00		0.00		0.00		0.0000	0.00		0.00		0.00		0.00		0.0000	0.00	
SD	0.00		0.00		0.00		0.00		0.0000	0.00		0.00		0.00		0.00		0.0000	0.00	
Median	0		0		0		0				0		0		0		0			
Q1	0		0		0		0				0		0		0		0			
Q3	0		0		0		0				0		0		0		0			
Min	0		0		0		0				0		0		0		0			
Max	0		0		0		0				0		0		0		0			
Prophylactic use																				
Total prophylactic FVIII utilization (IU)																				
Mean	0.00		0.00		0.00		0.00		0.0000	0.00		0.00		0.00		0.00		0.0000	0.00	
SD	0.00		0.00		0.00		0.00		0.0000	0.00		0.00		0.00		0.00		0.0000	0.00	
Median	0		0		0		0				0		0		0		0			
Q1	0		0		0		0				0		0		0		0			
Q3	0		0		0		0				0		0		0		0			
Min	0		0		0		0				0		0		0		0			
Max	0		0		0		0				0		0		0		0			
Total prophylactic FVIII utilization per participant per kg (IU/kg)																				
Mean	0.00		0.00		0.00		0.00		0.0000	0.00		0.00		0.00		0.00		0.0000	0.00	
SD	0.00		0.00		0.00		0.00		0.0000	0.00		0.00		0.00		0.00		0.0000	0.00	

Measures	Unadjusted										After IPTW									
	Roctavian Cohort		SoC Cohort		FVIII Sub-Cohort		Emicizumab Sub-Cohort		p-value (Roctavian vs. SoC)	Std. Diff. (Roctavian vs. SoC)	Roctavian Cohort		SoC Cohort		FVIII Sub-Cohort		Emicizumab Sub-Cohort		p-value (Roctavian vs. SoC)	Std. Diff. (Roctavian vs. SoC)
	N=		N=		N=		N=				N=		N=		N=					
	N	(%)	N	(%)	N	(%)	N	(%)	N	(%)	N	(%)	N	(%)	N	(%)	N	(%)		
Median	0		0		0		0		0.0000		0		0		0		0		0.0000	
Q1	0		0		0		0				0		0		0		0			
Q3	0		0		0		0				0		0		0		0			

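### Follow-up FVIII and emicizumab use is an un-annualised total in most places and annual in one; over all available follow-up, the total depends on how long each cohort is observed

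*Protocol*

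**What the plan says.** **Places that define a total**

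- Protocol 10.3.7.3: "The total FVIII per kg administered during follow-up will be compared between the cohorts", by a two-sample t-test. Protocol 7.2.5.2 asks for comparison over the total follow-up as well as over specific periods.
- SAP 7.9.4.3, opening: "Cumulative hemostatic medication use will be compared between the Roctavian and the following SoC sub-Cohorts", in IU/kg for FVIII and mg/kg for emicizumab. The amount per kg "will be calculated across the follow-up period and calculated between the Roctavian, SoC, FVIII, and emicizumab Cohorts", using the same follow-up approach as the primary ABR.
- SAP Table 5: prophylactic and on-demand amounts over time, in IU, mg, IU/kg or mg/kg, with no per-year unit.
- SAP shell Table 9: consumption rows without a per-year unit and without a split by follow-up duration (for example "Total prophylactic FVIII utilization per participant per kg (IU/kg").

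**The place that defines an annual amount**

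- SAP 7.9.4.3, later: "The total annual FVIII per kg during follow-up will be compared between the Cohorts". The next sentence drops the word annual: "Total FVIII per kg for any reason will be compared based on the absolute difference in the mean total FVIII per kg".

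**Measurement periods and the completeness rule**

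- SAP 7.9.4.3 lists the periods as "≥1 year of follow-up, ≥2 years of follow-up, ≥3 years of follow-up, all available follow-up".
- Protocol 10.3.7.3 and SAP 7.9.4.3 both limit the FVIII total to participants followed for the full time of the calculation.

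**The concern.** Two programmers working from this text could produce different outcomes, one in IU/kg and one in IU/kg/year. The unit also matters for validity. A total grows with observation time. If the cohorts are observed for different lengths of time, a difference in mean totals mixes dosing with follow-up, and the cohort observed for less time appears to use less product. ABR (SAP 7.9.3) and the infusion rate (AIR, in SAP 7.9.4.3 itself) are both divided by each participant's own time. FVIII and emicizumab amounts are not.

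**Working it through.** The documents give no numerical figure for consumption, so there is nothing to reproduce. The check has two parts.

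**1. Where unequal time can enter.**

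- *Fixed windows (1, 2 or 3 years).* The completeness rule keeps only participants who cover the window. If only use inside the window is counted, everyone contributes the same time and the total is a fair measure.
- *All available follow-up.* This is listed separately from the 3-year period, so it is meant to include people with less than 3 years. It has no common end point, so the completeness rule cannot equalise time.
- *Shell Table 9.* The rows for proportions of users are split into overall and at least 1, 2 and 3 years. The consumption rows are a single block with no duration, so the shell does not show which period they cover.

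**2. Size under the hypothetical estimand.** Inputs from protocol 10.3.2.3 and SAP 7.2.3: SoC time starts at index. Roctavian time for these outcomes starts at 5 weeks after infusion or 3 days after routine FVIII prophylaxis ends, whichever is later, or 27 weeks after emicizumab ends, and it is censored when prophylaxis resumes. Follow-up is capped at 3 years from index.

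Let r be annual use per kg and D the observed days.

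- Total = r × D / 365.25
- Annualised use = total / D × 365.25 = r
- At equal r, the ratio of totals = D(Roctavian) / D(SoC)

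SoC comparator: 3 × 365.25 = 1,095.75 days.

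| Roctavian observation | Days | Ratio of totals | Annualised ratio |
|---|---|---|---|
| Start 5 weeks late | 1,095.75 − 35 = 1,060.75 | 0.968 | 1.00 |
| Start 27 weeks late (assumes emicizumab ended at infusion) | 1,095.75 − 189 = 906.75 | 0.828 | 1.00 |
| Start 5 weeks late, censored at 2 years (assumed) | 730.5 − 35 = 695.5 | 0.635 | 1.00 |
| Start 5 weeks late, censored at 1 year (assumed) | 365.25 − 35 = 330.25 | 0.301 | 1.00 |

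The ratio does not depend on r, so no dose has to be assumed.

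**Treatment policy estimand.** Both cohorts start at index, and resumption of prophylaxis does not censor. Totals differ at equal use only if accrual or dropout gives the cohorts different follow-up. SAP 7.9.6 expects variable follow-up at the 36- and 54-month interims.

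**The case against.** The strongest reply is that the completeness rule is attached directly to the FVIII t-test in both documents. For fixed windows that reply stands. SAP 7.9.4.3 also limits interim and fixed-timepoint analyses to those with the specified follow-up, and SAP 7.9.6 limits 18-month comparisons to participants with at least one year. A reader might infer that every consumption comparison at every interim is confounded with follow-up; the documents do not support that.

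The reply can be extended: follow-up is capped at 3 years, so all available follow-up could be read as 3 years for everyone. That does not stand. The SAP lists the two periods separately. Under the hypothetical estimand, moreover, Roctavian time starts at least 5 weeks after index, so no Roctavian participant can reach 3 analytical years.

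The cross-reference to the ABR approach, together with the word annual, may mean that annualisation was intended. That is plausible, but the sentence stating the test, Table 5 and the shell all say otherwise.

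Two further points stand. Annualising is not neutral: short observation periods add variability, and under treatment policy they can inflate the Roctavian rate because prophylaxis continues in the first weeks after infusion. The stakes are also limited: this is one part of a secondary objective, SAP 7.9 calls secondary p-values nominal, and the time-adjusted AIR is compared alongside it.

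**Conclusion.** The point holds for the all-available-follow-up comparison and for the shell rows without a duration. It does not hold for fixed windows in which only in-window use is counted.

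Under the hypothetical estimand the distortion is structural and runs towards lower apparent Roctavian use: 3% from a 5-week later start, and about 37% if the participant is also censored at 2 years. The 2-year figure is an assumption, and all of these figures compare with a SoC participant observed for the full 3 years. Equal annual use is a benchmark, not a forecast. In IU/kg the distortion is the Roctavian cohort's own annual rate times the missing time, so it shrinks as that rate falls. Under treatment policy no size can be given from the documents, because it depends on differences in follow-up that are not yet known.

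A reader might also infer that the units undermine a comparison with baseline, which SAP Table 3 gives as "Total IU during the baseline period and annual utilization of FVIII concentrates expressed as IU/kg/year". The units do differ, but no change-from-baseline analysis of FVIII use is planned and baseline also reports a raw total, so this is a secondary matter of consistency.

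**What to change.** - For the all-available-follow-up comparison, define the outcome as amount per kg / observed days × 365.25, in IU/kg/year for FVIII and mg/kg/year for emicizumab. This matches the treatment of ABR and AIR.
- Keep raw totals only for fixed windows with complete follow-up, and state that only use inside the window is counted.
- Reconcile total and total annual in SAP 7.9.4.3, SAP Table 5, shell Table 9 and protocol 10.3.7.3. Give the shell 9 consumption rows a unit and a duration split.
- Report observed days by cohort beside the annualised result, and note its greater variability and, under treatment policy, the effect of the initial weeks on prophylaxis.

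The cost is wording in the protocol, the SAP and one shell. No new data are needed and clinical management is unaffected.

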7.9.4.4. Clinical Outcome Assessments

Population	Measurement Period	Analysis Notes
All participants with sufficient follow-up, comparing Roctavian Cohort to SoC Cohort; Participants without any COA scores will not be included	Assessments are expected to be conducted at baseline and every 6 months for quality of life and pain, and for joint health at least annually	For analyses of change from baseline, participants are expected to have baseline and at least one follow-up measure

The Hemophilia Joint Health Score (HJHS), Haemo-QoL-A, and Brief Pain Inventory – short form (BPI-sf) will be used as COAs. As these instruments standardize collection of data for areas that are monitored in routine clinical practice, the assessments are expected to follow routine clinical follow-up. Physicians participating in the AbD are expected to enter data for these instruments collected relative to the study index date per the operational definitions outlined in Table 5. The following Table 8 includes the assessment timepoints of interest throughout the follow-up and tolerance windows. If a participant has multiple measurements reported in the same window, the measurement closest to the time point of interest will be selected. An individual data point will only be utilized once in the analysis (e.g., if there is a measure at 1.2 years, this data point would only be used for 1 year and not the 2 year analysis).

Table 8. COA Timepoints of Interest and Tolerance Windows

Timepoints of Interest	Day of Assessment	Tolerance Window ¹
Baseline	Index date, day 0	0-91 days
6-months	Day 182	92-273 days
12-months (1 year)	Day 365	274-456 days
18-months	Day 547	457-638 days
24-months (2 years)	Day 730	639-821 days
30-months	Day 912	822-1,003 days
36-months (3 years)	Day 1,095	1,004-1,185 days

1. Tolerance windows are +/- 3 months before and after the expected assessment day.

Note: HJHS assessments will be completely annually, while Haemo-QoL-A and BPI-sf assessments will be completed every 6 months.

Descriptive statistics (mean, SD, median, IQR, minimum, maximum) will be used to summarize the COA scores at baseline, follow-up, and change from baseline. Two-sided t-tests will be used to compare the absolute change in scores from baseline between Roctavian and SoC Cohorts. Distribution of the outcome variables will be checked to make sure the assumptions of the two-sided t-test are met. If a skewed distribution is observed, a non-parametric Wilcoxon signed-rank test will be performed instead. SMD of the scores at baseline, follow-up, and change from baseline between the Roctavian and SoC Cohorts will also be estimated as the effect size measure.⁴⁸ SMD values will be classified into small, medium, large or very large based on the following ranges, 0.2-0.5, 0.5-0.8, 0.8, and ≥1.3.

Participants with an evaluable baseline score and at least one evaluable post-baseline score will be included in the change from baseline analyses. Since participants are expected to have follow-up visits every 6-months for Haemo-QoL-A and BPI-sf and annual follow-up visits for HJHS, it is expected that COAs will be measured with a maximum of seven time points for Haemo-QoL-A and BPI-sf (baseline, 6±3, 12±3, 18±3, 24±3, 30±3, and 36±3 months) and four time points (baseline, 12±3, 24±3, and 36±3 months) for HJHS. The last follow-up measure will be used in the change from baseline analysis. The last follow-up measure may be required to have occurred at least a certain

number of years after baseline to increase interpretability of results. A general linear mixed model with unstructured covariances will be fit to conduct a longitudinal analysis for each COA outcome. The mixed model is chosen to account for the repeated measures, while allowing flexibility for any potential missing values. No missing data will be imputed. The explanatory variables that will be included in the model are treatment (Roctavian vs. SoC) and time. Treatment by time interaction will also be included in the model to assess whether the treatment effect changes across time. Residual analysis will be conducted to ensure the independent and identically distributed random variables assumptions of the model residuals are met. Regression coefficients, 95% CIs and P-values for each of the fixed-effects parameters will be reported. Estimated correlation matrix will also be reported to assess the correlation of the outcome between each time point.

For all the COA outcomes described above, both the unweighted and IPTW weighted analyses will be conducted. SMD will be computed to compare the outcomes between Cohorts. P-values for each corresponding statistical test will also be reported.

In addition, a responder analysis will be considered for the COA improvement and deterioration of the six joint health scales to understand the magnitude of observed clinically meaningful effects. A responder analysis is defined as an analysis or presentation of the proportion of participants who achieved a pre-defined level of improvement on one of the main outcomes at a certain time point.⁴⁹ Based on IQWiG's guidance for responder analysis, (a 15% change of the scale range)⁵⁰, participants with a deterioration and improvement (reported separately) in their scores of 15% (e.g., 15% of a 10 point scale is 1.5) from the baseline to the latest follow-up measure will be defined as responders. All other participants will be defined as non-responders. The binary outcome (responder versus not) will be analyzed using propensity score IPTW weighted log binomial regression models. The main predictor of interest is the treatment effect (Roctavian vs. SoC), other imbalanced covariates after propensity score adjustment may be included in the model as necessary. The risk ratio (relative risk), corresponding 95% CIs and p-values will be reported.

To visually represent the responder analysis results and to aid in its interpretation, The response rate at each time point will be plotted as response curves for each COA by study Cohort to illustrate the change in response rate across time.

